4.1 General Design

- A phase III, randomized, two-arm trial with a wait-list control group
- The intervention itself is 10 weeks, with an additional five week follow up assessment for those in the exercise arm to determine adoption of the program. Overall, the anticipated total duration should be 20 weeks for participants
- The intervention will consist of (a) an initial in-person instructional session; (b) instructional materials and resistance training equipment (e.g., resistance bands) and (c) support and feedback provided via video coaching sessions; and (d) a final in-person study visit to collect post-study measures for both groups

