4.1.3 Primary Safety Endpoints

The primary safety endpoint will be total number of adverse events over the duration of the intervention.

5 Study Infrastructure

The general infrastructure for this study will include an overall PI ([name]). There will be additionally one primary biostatistician for the study, and one main study coordinator who will be responsible for managing daily study operations.

6 Study Subjects – Enrollment and Withdrawal

- Accrual Goal: The study aims to enroll 40 participants over a one-year period. Subjects will be identified through their clinician/oncologist to determine interest in the study before being screened over the telephone by study staff.
- Participants will be screened over the phone to determine eligibility, and enrollment in the study will occur after screening by both the clinician/oncologist and research staff. The screening procedures will be performed under a separate screening consent form.

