Table 2. Series of exercises, with progressions and regressions to increase/decrease difficulty.

Primary muscle group	Exercise	Progressions	Regressions
Thighs (quadriceps, hamstrings)	Body weight squats	
• Add resistance band• Holding dumbbells	
• Chair squats• Shortened range of motion
Calves (gastrocnemius, soleus)	Standing heel raises	
• Holding dumbbells• Elevate ball of foot	
• Shortened range of motion
Chest (pectoralis major & minor)	Standing chest press	
• Increase band tension	
• Reduce band tension
Back (trapezius, latissimus dorsi)	Seated banded row	
• Standing row• Increase band tension	
• Reduce band tension• Shorten range of motion
Abdominals (rectus & transversus abdominus)	Static v-sit hold with feet on floor	
• Elevate feet• Add rotation• Add dumbbell	
• Support with hands• Add lumbar support w/ towel
Shoulders (deltoids)	Seated banded press	
• Standing• Use dumbbells	
• Reduce band tension• Shorten range of motion
Biceps brachii	Seated banded curl	
• Standing• Add tension to band• Use dumbbells	
• Reduce band tension• Shorten range of motion
Triceps brachii	Seated arm extension	
• Increase band tension	
• Reduce band tension

During the study period, participants in the intervention arm will be instructed to complete the exercise routine twice a week for 10 weeks during the intervention, and also continued throughout the five week follow up period. There are eight video calls with the study coordinator to check in, to identify any issues or concerns with the exercises, and to finally monitor progress in the form of assessing volume/intensity/difficulty of each of the exercises. These calls are done over video so that the coordinator can build rapport with participants, and that participants can show

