or demonstrate issues with exercises or their form. At the mid-point of the study, participants will receive an email with the questionnaires, so that the questionnaires will be done at baseline, at the study mid-point, and at the final visit.

Participants in the intervention group will also complete accelerometer (Actigraph) assessments at three study points: Early in the intervention near the instructional visit, at the mid-way (5-week) mark, and before the final visit. These accelerometers will be sent and received via mail and participants will receive instructions on how to wear, use and send to us during the instructional visit.

At the end of the 10 week period, participants will return to the UW campus for a final visit to repeat baseline study measures. At this time, intervention arm participants will also complete an exit-style interview with the study coordinator to help improve the intervention for future participants. This will be recorded, but anonymized upon transcription.

While the formal intervention period will be 10 weeks in duration, we will continue to follow those in the exercise arm for five weeks post-final assessment. This follow up period will consist of surveys to the participants assessing the frequency of the home-based resistance exercise, to determine if the behavior of exercise persists in the short-term following intervention conclusion.

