 - **When collected:** Baseline, mid-point (~5 weeks), final visit (~10 weeks)
- **Self-efficacy.** This will be assessed using the validated self-efficacy for exercise scale, modified for specificity to strength training.³⁴ These measures will be repeated at the study mid-point (5 weeks) to assess changes over time.
 - **When collected:** Baseline, mid-point (~5 weeks), final visit (~10 weeks)
- **Adherence.** Compliance and adherence will be measured via detailed exercise logs. A participant needs to complete at least 50% of the prescribed exercises in a session to be considered adherent to the session.
 - **When collected:** ongoing, logs will be completed throughout the intervention and submitted at the final visit
 - Additionally, for those in the intervention arm, we will ask that they continue to conduct the prescribed exercises for an additional five weeks after study completion. Participants will still submit paper logs, and this adherence measure will allow for study of adherence without prescribed check-ins from the study coordinator over the five week period.
- **Acceptability.** Participants will participate in a semi-structured qualitative interviews with the study coordinator. Interviews will be recorded, transcribed and coded to identify content themes. These interviews will be used to collect qualitative information and overall satisfaction with the intervention, as well as areas to improve with future interventions and barriers to participation.
 - **When collected:** Final visit (~10 weeks)

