9.3 Subject Population(s) for Analysis

The populations for this investigation include:

- All-randomized population: Any subject randomized into the study, regardless of whether they received study agent
- All-treated population: Any subject randomized into the study that received at least the instructional visit of the intervention
- Protocol-compliant population: Any subject who was randomized, was allocated to the exercise group and provided at least one set of data elements required by the protocol.

9.3.1 Describe the types of analysis:

- **Primary Analysis:** The primary objective includes measuring the percentage of completed sessions compared to prescribed, and a one-sample t-test will be conducted to determine if that proportion, across participants, is >90%. A one-sample t-test will be done to determine if retention is >90%.

- **Secondary Analyses:** The secondary analyses includes measuring the objective and functional changes from pre to post intervention as well as differences between groups. Paired ANOVAs and descriptive statistics will be used to analyze functional and objective data, as well as participant feedback data, including satisfaction with each component of the intervention.
- **Exploratory, longitudinal analyses:** Content analysis will be done on the qualitative interviews to examine barriers to physical activity, as well as satisfaction with the intervention, and identification of themes to improve the intervention. Although formal hypothesis testing is not part of our specific aims, we will conduct longitudinal analyses of the data we collect to estimate potential magnitude of expected changes, as well as longitudinal analysis of the repeated measures.
- **Safety Analysis:** The safety analysis includes simple descriptive analysis about the number of adverse events over the course of the intervention between groups and across sites.

9.4 Planned Interim Analysis:

There are no planned interim analyses for this investigation.

10 Data Collection, Handling and Record Keeping

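### Adverse events during study-directed training in weeks 11-15 enter no stated safety endpoint or analysis, although Table 3 schedules a safety assessment at week 15

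*Combined protocol and SAP*

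**What the plan says.** **Safety window.** Section 4.1.3 defines the endpoint: "The primary safety endpoint will be total number of adverse events over the duration of the intervention". The safety analysis in 9.3.1 is descriptive and covers the "number of adverse events over the course of the intervention between groups".

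**Length of the intervention.** Section 4.1: "The intervention itself is 10 weeks, with an additional five week follow up assessment for those in the exercise arm". Section 8 (Exercise interventions) agrees: "While the formal intervention period will be 10 weeks in duration, we will continue to follow those in the exercise arm for five weeks".

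**Training after week 10.** Section 8 tells exercise-arm women to do the routine "twice a week for 10 weeks during the intervention, and also continued throughout the five week follow up period". Section 8.1 (Adherence) says the same as a request: "we will ask that they continue to conduct the prescribed exercises for an additional five weeks after study completion". It gives the purpose as studying "adherence without prescribed check-ins from the study coordinator over the five week period".

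**Safety collection.** The study calendar (Table 3) ticks safety at 4-6, 10 and 15 weeks.

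**Wait-list arm.** Section 8 gives this arm no follow-up beyond the 10-week visit, and 8.4.4 gives it the introductory session at that visit.

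**The concern.** The five weeks after the final visit are more than passive follow-up. The protocol directs the exercise arm to go on training, so this is exposure that the study itself generates. It is also the phase with the least contact. The last planned call is in week 8 (8.2 and Appendix 1), and Sections 10.4 and 11 present check-in calls as the way physical problems are picked up and dealt with.

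For a home programme meant to lead to a larger trial, how women tolerate training once coaching stops is part of what the pilot should report. With the window as stated, an injury in week 12 could be recorded at week 15 and still not count in the trial's safety result. Whether to report it would be decided after the data are seen.

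**Working it through.** The documents give no adverse-event rate, safety sample size or exposure total, so there is no stated figure to reproduce. The check compares the windows and then counts exposure.

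**Windows side by side**

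| Item | Weeks 1-10 | Weeks 11-15 |
|---|---|---|
| Training instructed, exercise arm (8, 8.1) | yes | yes |
| Coordinator check-ins planned (8.1, 8.2) | yes, the last in week 8 | none |
| Safety ticked (Table 3) | 4-6 and 10 weeks | 15 weeks |
| Wait-list arm observed (8) | yes | no |
| In the safety endpoint (4.1.3) | yes | no |
| In the safety analysis (9.3.1) | yes | no |

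The longitudinal analyses in 9.3.1 do not mention safety, so they do not take up the week-15 data either.

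**Inputs**
- Two sessions per week, for 10 weeks and then 5 more (Section 8).
- 40 women allocated 1:1 (Sections 6 and 8.5), so about 20 in the exercise arm.
- 90% adherence in weeks 1-10, the protocol's own hypothesis under Aim 2.
- Adherence in weeks 11-15: not given. I assume 30% to 100%.

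**Prescribed exposure per woman**
- Weeks 1-10: 2 × 10 = 20 sessions.
- Weeks 11-15: 2 × 5 = 10 sessions.
- Share outside the endpoint: 10 / (20 + 10) = 33.3%.

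**Prescribed exposure in the arm (about 20 women)**
- Inside the window: 20 × 20 = 400 sessions, and 20 × 10 = 200 person-weeks.
- Outside it: 20 × 10 = 200 sessions, and 20 × 5 = 100 person-weeks.
- Total: 600 sessions and 300 person-weeks.

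**Performed exposure**

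With adherence a in weeks 11-15, the omitted share is 10a / (20 × 0.9 + 10a) = 10a / (18 + 10a).

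| a (assumed) | Calculation | Omitted share of performed sessions |
|---|---|---|
| 30% | 3 / 21 | 14% |
| 50% | 5 / 23 | 22% |
| 70% | 7 / 25 | 28% |
| 90% | 9 / 27 | 33% |
| 100% | 10 / 28 | 36% |

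**Visit window.** Table 4 lets the final visit fall two weeks either side of its date. If training simply runs from the start to five weeks after that visit, the omitted share of weeks is 5 / 13 = 38% for a visit at week 8 and 5 / 17 = 29% for a visit at week 12. The result stays near one third.

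**Events.** Turning a share of exposure into a share of events needs an event rate in each phase. The documents give none.

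**The case against.** The strongest defence is that 4.1.3 defines only the primary safety endpoint, and limiting it to the controlled period is sound. After week 10 the wait-list arm is no longer followed and has had its introductory session, so a between-arm count would compare unequal observation. This stands, and the 10-week comparison should be kept. It does not prevent a one-arm descriptive table, since 9.3.1 plans only description.

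A second defence is that late harms are not ignored. Safety is scheduled at week 15, the investigator reviews adverse events, and unanticipated problems go to the IRB (10.4). A reader might infer that the plan means to discard late harms, and the documents do not support that. But monitoring and IRB reporting do not place these events in the trial's safety result.

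Third, the wording may be loose: the Study Summary lists the five-week follow-up in the regimen row. Sections 4.1 and 8 weigh against a 15-week intervention. Even on that reading, a between-group count would set 15 weeks of observation against 10, and the window would still have to be stated.

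A reader might also infer that a third of training-related events would be missed. That requires a constant event rate, for which the documents give no support. Musculoskeletal soreness, a named training risk in 2.3.1, need not occur evenly over 15 weeks. The 33% is prescribed exposure only, and the follow-up exists partly to learn whether women keep training.

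Finally, a plain person-week rate for weeks 11-15 set beside weeks 1-10 could reassure falsely. Without check-ins fewer events may be noticed, and fewer sessions per week would lower the rate per person-week even if the risk per session were unchanged.

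**Conclusion.** The point holds in limited form. The stated safety window ends at week 10 while instructed training and scheduled safety collection run to week 15, and no endpoint or analysis takes up the later events. The omission is 33% of prescribed sessions in the exercise arm, or about 14% to 36% of performed sessions under the adherence assumptions above. The share of adverse events omitted cannot be derived from the documents.

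This is a minor improvement. The primary endpoint (adherence) and the 10-week between-arm safety comparison are unaffected, and the trial is a descriptive pilot. The gap is an incomplete safety summary for the exercise arm.

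One uncertainty concerns collection. Section 8 describes the follow-up surveys as measuring how often women exercise, and the Appendix 1 checklist has no week-15 line. Only Table 3 shows a week-15 safety item. The survey form itself is not in the text available, so I do not conclude that the question is missing, only that it needs confirming.

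**What to change.** 1. Keep the between-arm comparison of adverse events at 10 weeks, and state that window in weeks in 4.1.3 and 9.3.1.
2. Add to both sections a separate descriptive exercise-arm tabulation for weeks 11-15, and cumulatively for weeks 1-15. Give the number of women with events, the number of events, and both logged sessions and person-weeks as denominators. The paper logs in 8.1 supply the sessions.
3. State with the table that the two periods differ in ascertainment because check-in calls stop, and that weeks 11-15 have no concurrent control. A lower rate in the later weeks should not be read as evidence of greater safety.
4. Confirm that the week-15 safety item in Table 3 is asked in the follow-up survey, and add a week-15 line to the Appendix 1 checklist.
5. While editing, reconcile the 20-week total duration in 4.1 with the 15-week calendar. This does not change the conclusion.

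Cost: one small table, a few sentences and, if the safety question is not yet asked, one survey item. No change to sample size, visits or the primary analysis.

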6.1 Subject Population

Age range of participants include ages 18-74 which is the range where diagnosis of endometrial cancer is most common. Because we intend to study adults, and not geriatric populations, the upper cap on the age for this study is 74 as to not dilute or modify the effect of resistance training in adults compared to elderly populations.

Women are the only participants in this study as endometrial cancer doesn't afflict men. No minorities or ethnic groups will be excluded from this study. We will recruit subjects without regard for minority status and ethnic status will be coded according to the Office of Management and Budget (OMB) Directive No. 15. The estimated ethnic/racial composition is presented in the Targeted/Planned Enrollment table and is representative of women in the geographic area of the proposed study (2010 Census Data for Madison, WI: 79% white, non-Hispanic; 7% African American; 7% Hispanic or Latino; 7% other ethnic/racial identities).

6.2 Inclusion Criteria

Inclusion Criteria	
1	Willing to provide written informed consent
2	Willing to comply with all study procedures and be available for the duration of the study
3	Fluent in spoken and written English
4	Women 18-74 years of age
5	Documented diagnosis of Type I, stage I-IIIc endometrial cancer within the past 5 years
6	Completion of current treatment for endometrial cancer, period of time of ≥ 10 weeks from treatment completion to study enrollment is required

6.3 Exclusion Criteria

Exclusion Criteria	
1.	Absolute contraindications to exercise (i.e., acute myocardial infarction, severe orthopedic or musculoskeletal limitations)
2.	Have evidence of recurrent or metastatic disease
3.	Are currently performing resistance training ≥ 2 days per week
4.	Report of chest pain, shortness of breath, fainting, or angina pectoris
5.	Have physical disability that would limit range of motion through exercises such as sitting, standing and inability to walk one block
6.	Plans to move from the area
7.	Enrolled in another clinical trial or has used of any investigational drugs, biologics, or devices within 30 days prior to randomization
8.	Women who are pregnant or breast-feeding
9.	Not suitable for study participation due to other reasons at the discretion of the investigator

6.4 Subject Screening for Recruitment

6.4.1 Subject Identification

Participants will be recruited primarily through referrals at the research site. At the primary site, it will be UW-Madison's gynecologic oncology clinic, assisted by the UW Carbone Cancer Center's Gynecology Disease Oriented Team (DOT), a group that supports accrual to both collaborative and investigator-initiated clinical trials. Potentially eligible patients will be identified by the clinician after primary treatment has been completed and initial contact will be made by a member of the study team with endorsement of the medical care team. If needed, recruitment will be augmented via outreach through local cancer support organizations. Patients referred by their physician will be

contacted by study staff and screened for eligibility over the telephone. Self-referred participants will undergo telephone screening first, then eligibility will then be confirmed with the woman's physician. Recruitment methods will be the same between potential subject groups, i.e. same in treatment and wait-list control groups.

Additionally, members of the clinical care team may identify eligible cancer survivors from the electronic health record (EHR) and provide contact information for potentially eligible individuals to members of the study team. The study team will mail a letter to these individuals inviting them to participate, and providing them with information on how to contact the study team to enroll or to opt out.

Should we encounter difficulties with recruitment, we may accrue participants through community-based strategies including posting fliers at partnership organizations (such as Gilda's Club, for example). The primary mechanism of subject identification will be through referrals at the research site, but if necessary we may deploy community, word of mouth and flier-based recruitment.

6.4.2 Permission to Contact Form

Participants will be identified and recruited primarily through referrals at the research site, and prospective participants who are interested in the study will be asked to sign a Permission to Contact Form (Appendix 7) which allows members of the research team to contact them. Those who would like to be contacted to learn more about the study will sign the permission to contact form at the clinical site, and then those forms will be delivered to members of the research team to contact and screen for eligibility for the study. Once the permission to contact form is signed, the research team will take over to confirm eligibility, screen over the phone and enroll in the study.

6.4.3 Recruitment and Retention Strategies

Participants will be recruited primarily through referrals at the research site. If necessary, participants may be recruited through community partnerships through fliers and word of mouth recruiting.

Because the intervention is only 10 weeks in duration with a five week follow up, we do not anticipate major issues with participant retention. We have experience conducting several previous PA trials in cancer survivors and typically observe only ~5% loss to follow-up in a short-term study. To encourage retention, participants will receive \$50 compensation at the baseline visit and again at the 10-week follow-up visit.

7.5 Vulnerable Populations

No vulnerable populations will be included in this study design.

TABLE 1: Vulnerable populations included and excluded from this study

Include	Exclude	Vulnerable Population Type
	X	Adults unable to consent
	X	Individuals who are not yet adults (e.g. infants, children, teenagers)
	X	Wards of the State (e.g. foster children)
	X	Pregnant women
	X	Prisoners

7.5.1 Subject Capacity

All subjects will have the capacity to give informed consent, else they will be excluded from this study.

7.6 Informed Consent

The PI will be responsible for ensuring that valid consent is obtained and documented for all subjects unless the IRB waives the requirement for documentation of informed consent for all or part of the study. Verbal consent will be given for the telephone screening questionnaire; however for the intervention, informed consent will be obtained during an in-person visit.

7.6.1 Process of Consent

- Consent will be obtained by either the PI, or by the Study Coordinator.
- Consent will be documented by having the participant sign the form, with a member of the study team signing to affirm the witnessing of the signing. One copy will be made and given to the participant, with another kept by the study team. Documentation will be stored in each participant's individual research file at the site's pre-determined storage location.
- Informed consent will be structured to be conducive to rational and thoughtful decision making by asking the prospective participant several questions about the intervention, including how to withdraw, how the groups will be allocated, what participation consists of, as well as what are the alternatives to participation.

